## 6.3 Exclusion criteria

- Be indigenous;
- Active TB or previous use of INH;
- Sscore AUDIT  $\geq 15$ .
- Reactive serology for HIV, hepatitis B and C;
- Reactive result for IGRA, considering as positive the result of TB1 Tube and / or TB2 Tube above 0.2 IU/mL(53);
- Liver enzymes (AST and ALT) three times the upper limit;
- History or treatment for epilepsy;

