## 6.4 Indications for premature exclusion

The participant may be withdrawn from the clinical trial at any time for the reasons listed below:

- at the request of the participant (withdrawal or withdrawal of consent);
- non-compliance with the protocol;
- interruption of treatment or sum of temporary interruptions of intervention  $\geq 90$  days, either by decision of the participant or at medical discretion;
- transfer to another prison unit or early release;
- Clinical or laboratory AE requiring permanent discontinuation of medication (according to study-specific SOP);
- any exclusion criterion according to item 5.3 that, incidentally, arises during the follow-up (both recently diagnosed and not previously recognized);
- use of acetaminophen, valproic acid, carbamazepine, cycloserine, ethionamide, corticosteroids, diazepam, triazolam, disulfiram, phenytoin, aluminum hydroxide and rifampicin which, at the discretion of the investigator, are used in a dose that may interfere with the efficacy of INH as medication;
- another reason, at the discretion of the principal investigator or study coordinator.

At the time of the participant's withdrawal, a premature exclusion visit with clinical evaluation, evaluation of AE and blood and / or sputum collection should be performed according to the clinical judgment, according to the study schedule (figure 1).

In addition, for cases in which treatment has been interrupted by decision of the participant or at medical discretion, as of 6 months from the start of the DOT, the participant will have two options: to remain in the study without the intervention (DOT), but with the accomplishment of all the visits anticipated in the protocol or to leave completely of the study without the realization of

additional collections and other accompaniments. For the latter case, follow-ups will be carried out only if the participant presents some AE at the time of their withdrawal.

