## 6.5 Conducting the study

Participants will be invited to participate in the clinical trial through the consent process and will agree to participate in the study by signing the ICF.

In the recruitment interval, prior to any intervention, participants will respond to the AUDIT questionnaire - which assesses various levels of alcohol use, from safe use to likely dependence - and eligibility criteria will be checked. In the recruitment interval, participants will have a 9mL sample of peripheral blood collected for testing of IGRA (QuantiFERON® TB GOLD PLUS kit - Qiagen, HIV, hepatitis B (HBsAg) and C (Anti-HCV) and serum levels of liver enzymes (AST and ALT).

After the results of these initial tests (HIV, hepatitis B and C, IGRA, AST and ALT), if eligible, the participant will answer questionnaires containing socioeconomic, medical and criminal history and have a sample of sputum collected for culture.

The participant will be included in the study without the result of the culture and, in case of a positive result for Mtb, the intervention will be suspended, the same will be excluded from the study and treated according to the MS protocol. If the sputum culture is contaminated, a new sample should be collected within 30 days after the result.

The recruitment interval will last 20 to 45 days.

On the day of initiation of DOT (D0), each participant will receive a supervised dose (three oral tablets) of INH (900mg) or placebo. The same will happen twice a week for 12 months. During the DOT the participant will be asked about AE.

Blood samples will be collected every three months after D0 to measure hepatic enzyme levels (AST and ALT), as well as clinical evaluation and verification of AE, as shown in figure 1.

At six months and at the end of the intervention (12th month), all participants will have a sample of sputum collected for culture and a blood sample for detection / quantification of interferon gamma. The same evaluation will be repeated in the 24th month counted from D0, that is, one year after the end of the intervention.

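### A permanent drug stop before month 6, such as for an enzyme rise at the month-3 test, carries no offer to stay in follow-up and puts the participant outside the intention-to-treat set

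*Combined protocol and SAP*

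**What the plan says.** **Withdrawal (6.4).** The list is permissive: "The participant may be withdrawn from the clinical trial at any time for the reasons listed below". Three of its grounds can apply to a liver-enzyme rise:

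- "Clinical or laboratory AE requiring permanent discontinuation of medication (according to study-specific SOP";
- "interruption of treatment or sum of temporary interruptions of intervention" totalling 90 days or more;
- "any exclusion criterion according to item 5.3 that, incidentally, arises during the follow-up (both recently diagnosed and not previously recognized". Section 5 has only 5.1 and 5.2, so 6.3 is evidently meant. One of the 6.3 criteria is "Liver enzymes (AST and ALT) three times the upper limit".

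**At withdrawal.** In 6.4, "blood and / or sputum collection should be performed according to the clinical judgment". Figure 1 shows IGRA at the early exclusion visit in parentheses, which its legend defines as optional.

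**Staying in off drug.** Where treatment is stopped by the participant or on medical grounds, "as of 6 months from the start of the DOT, the participant will have two options": keep all planned visits without the drug, or leave entirely. Nothing equivalent is written for an earlier stop.

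**Monitoring (6.5).** "Blood samples will be collected every three months after D0 to measure hepatic enzyme levels". Treatment is interrupted for clinical signs of hepatotoxicity or, without symptoms, for enzymes above five times the upper limit. The first IGRA after baseline is at month 6.

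**Analysis (6.6).** The intention-to-treat analysis takes only participants with six or more months of treatment. Latent TB conversion is defined on the month-12 or month-24 result.

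**The concern.** Month 3 is the only scheduled liver test before month 6. If it leads to a permanent stop, the plan offers that person no off-drug follow-up. It requires no IGRA at exit, and an exit IGRA would not meet the month-12 or month-24 outcome definition in any case. Section 6.6 then leaves the person out of the primary comparison whether or not follow-up continues.

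The cause of the stop is an expected effect of one arm's drug, so the people dropped may come mainly from the isoniazid arm. An analysis set defined by time on treatment then no longer compares the groups as randomised. The outcome chiefly affected is the IGRA primary outcome, since 6.5 also uses the notification system to find active TB.

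**Working it through.** **Inputs.** Risks of 20% (placebo) and 10% (isoniazid), 5% significance, 90% power, 560 participants raised to 728 (6.1.1); 364 per arm (6.1.2). Hepatitis 0.52% on treatment and 0.12% in controls; hepatotoxicity 2.4% and 2.7% in two randomised trials and 6% on average in a review of prison studies (2.5); 1% (6.9). Upper limits of AST 40 and ALT 30 IU/mL (6.5).

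**The plan's own figure.** The pooled two-sided formula is n = [1.96 √(2 × 0.15 × 0.85) + 1.2816 √(0.20 × 0.80 + 0.10 × 0.90)]² / 0.10² = 266 per arm, or 532 in total. With continuity correction it is 286 per arm, or 572, which is 2.1% above 560; the unpooled corrected form gives 566. The stated 560 is thus reproduced to within about 2%. 560 × 1.30 = 728, and 728 / 2 = 364.

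**Path of a permanent stop at month 3.**

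1. Withdrawal is allowed under 6.4 but not required.
2. If withdrawn: no offer to stay, and IGRA optional.
3. If kept in: visits can continue, but the person has about three months of treatment, and 6.6 asks for six. The person is outside the set on either branch.

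**Illustrative size, enzyme path only.** The documents give no rate of enzyme rises before month 6, so the hepatitis and hepatotoxicity rates stand in. Let f be the share of the isoniazid arm removed, taking all such events as falling before month 6, which is an upper bound. Let r be the conversion risk of those removed. The analysed risks are 10% and 20%. Anyone removed from placebo is assumed to convert at 20%, so that arm does not change.

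All-randomised isoniazid risk = (1 − f) × 10% + f × r; RR = that risk / 20%; NNT = 1 / (20% − that risk).

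With r = 20%:

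| f | people of 364 | isoniazid risk | RR | NNT |
|---|---|---|---|---|
| 0.52% | 1.9 | 10.05% | 0.503 | 10.05 |
| 1% | 3.6 | 10.10% | 0.505 | 10.1 |
| 2.4% | 8.7 | 10.24% | 0.512 | 10.2 |
| 2.7% | 9.8 | 10.27% | 0.514 | 10.3 |
| 6% | 21.8 | 10.60% | 0.530 | 10.6 |

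The control figure gives 0.12% × 364 = 0.4 people on placebo.

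With r = 10%, RR = 0.50 for every f. Under the linear accrual of risk assumed in 6.7, a month-3 stop gives r = 3/12 × 10% + 9/12 × 20% = 17.5%. RR is then 0.504 at 1% and 0.5225 at 6%.

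Starting instead from a true RR of 0.50, the analysed RR is [(10% − f × r) / (1 − f)] / 20%. With r = 20% this is 0.495 at 1%, 0.486 at 2.7% and 0.468 at 6%, so the direction is the same.

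**Power.** With 280 per arm it is 0.914; with 6% removed from both arms it is 0.897. The issue is comparability, not numbers.

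**Enzyme limits.** Three to five times the upper limit is AST 120 to 200 (3 × 40, 5 × 40) and ALT 90 to 150 (3 × 30, 5 × 30) IU/mL. In that band an asymptomatic person meets a 6.3 criterion but not the 6.5 rule for interruption.

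**The case against.** **Removal is not automatic.** This stands. Section 6.4 says may, 6.5 requires only that treatment be interrupted and care given, and an interruption under 90 days is not a ground under the interruption bullet. Six months of treatment is not defined as doses or elapsed time, so someone who stops briefly and resumes may still qualify. The point is firm only for a permanent early stop, and there the 6.6 rule applies even if nobody is withdrawn.

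**A reader might infer that 6.4 requires withdrawal at three times the upper limit, against 6.5.** The documents do not support this. The bullet is general and permissive, its wording suits new diagnoses such as HIV, and 6.5 is the specific rule for follow-up. Read literally, it would also carry the 0.2 IU/mL IGRA entry cut-off into follow-up, where 6.5 and 6.6 use the manufacturer's. The study SOPs may settle the band, but they were not among the documents. What remains is a wording clarification.

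**A reader might infer that the enzyme path seriously distorts the primary result.** The figures do not show that. The 6% comes from a prison review that included people with HIV. This trial excludes HIV, hepatitis B and C, AUDIT scores of 15 or more and age 45 and over, and 2.5 names age above 45 and alcohol as risk factors for hepatitis.

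**The 6.6 rule reaches far beyond enzyme cases.** True: it drops every early stopper. That is a reason to widen the remedy. An exception for enzyme stops alone would make the analysis set depend on the reason for stopping, a post-randomisation event expected mainly on isoniazid.

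**The 30% allowance and the partial-consent sentence in 6.6 already cover this.** They do not. The allowance protects numbers, not balance. The consent sentence concerns the participant's own decision, not a medical stop, and does not waive the six-month rule.

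**Conclusion.** The point holds in this form: a participant permanently taken off drug before month 6 is not offered off-drug follow-up, may have no IGRA outcome, and is excluded from the analysis labelled intention-to-treat. This follows from stated rules in 6.4 and 6.6, not from missing detail.

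Through the enzyme path alone the bias is probably small. An analysed RR of 0.50 would be too favourable by about 0.005 at the protocol's own 1%, and by up to 0.03 at 6%. This assumes that all events fall before month 6, that only the isoniazid arm's risk is affected, and that those removed would convert at between 10% and 20%. The true number affected cannot be derived from the documents. A conversion risk above the placebo rate would enlarge the bias, but nothing in the documents suggests one. The calculation does not cover other early stoppers whom 6.6 also drops.

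The change is worth making because it is cheap and restores the comparison as randomised.

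**What to change.** 1. **6.4:** delete the month-6 condition. Anyone whose drug is stopped, at any time and for any reason, is asked to stay for the scheduled IGRA and sputum culture at months 6, 12 and 24, unless consent is fully withdrawn.
2. **6.6:** replace the intention-to-treat sentence. The analysis includes all randomised participants in their assigned arm, whatever their time on treatment. State how missing outcomes are handled. Keep the set with six or more months of treatment only as a secondary, modified analysis.
3. **Minor clarification in 6.4:** correct item 5.3 to 6.3, and state that the three-fold AST/ALT limit applies at entry only, with 6.5 governing follow-up.

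The cost is a protocol amendment with ethics review, a few more off-drug participants to follow at visits already scheduled, some missing outcomes to handle, and possibly a slightly diluted effect estimate.

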## **2.5 Isoniazid in the treatment of latent TB**

In 1999, Smieja et al.(35), in a review to identify the efficacy of INH in non-HIV subjects, found that the relative risk of acquiring TB after 6 months of prophylaxis with 300mg of the drug was 0.40 (95% CI 0.31 -0.52), with an absolute risk reduction of 0.01, ie, it would take 100 treatments to avoid 1 case of active TB. The most frequent adverse reactions were mild and transient headache, nausea, dizziness. The occurrence of hepatitis was 0.12% in the controls and 0.52% in the treatments, having as risk factors age greater than 45 years and alcohol use.

Sharma et al.(36) in a review comparing regimens with rifamycin (and its derivatives, including rifapentine) and INH, conclude that regimens using rifamycin alone are longer, have a lower completion rate, and do not present advantages over the INH regimen alone.

Epidemiological conditions conducive to high TB transmission are currently found in the prison system (26). Macintyre et al.(37) conducted a cohort study in 16 of the 23 prisons in Maryland and concluded that the use of INH prophylaxis reduced the risk of progression to active TB in individuals reacting to the skin test by 50%. Al-Darraj; Kamarulzaman and Altice(38) have shown, through a systematic review covering 18 publications (between cohort and transverse studies) that the efficacy in cases of latent TB is about 60% in non-HIV individuals and 36% in individuals with HIV, using INH for 6 months. The hepatotoxicity rate was on average 6%. Approximately two-thirds of these studies were conducted in countries with low endemicity for the disease. In view of this, the authors recommend that further studies should be conducted, but in countries highly endemic for the disease, to explore the efficacy and safety of INH in closed prisoners.

Two randomized clinical trials showed an 83.8% and 69% adherence rate with an isolated INH regimen and a hepatotoxicity of 2.4% and 2.7%(39,40). It is noteworthy that in the aforementioned studies all the individuals allocated in the treatment group had latent TB diagnosed through the skin test with PPD.

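### Section 6.4 lets a participant be taken out of the trial, not only off study drug, for use of listed concomitant drugs, so a measurable primary outcome can be lost after randomisation

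*Combined protocol and SAP*

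**What the plan says.** Section 6.4 opens its list of reasons with "The participant may be withdrawn from the clinical trial at any time for the reasons listed below". One reason is "use of acetaminophen, valproic acid, carbamazepine, cycloserine, ethionamide, corticosteroids, diazepam, triazolam, disulfiram, phenytoin, aluminum hydroxide and rifampicin which", and the sentence ends "at the discretion of the investigator, are used in a dose that may interfere with the efficacy of INH as medication". The rule is therefore permissive, needs a judgement about dose, and removes the person from the trial.

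What happens next is set in three other places:

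- Figure 1 (Section 6.5) marks IGRA and sputum collection at the early exclusion visit as optional.
- The last paragraph of Section 6.4 lets a participant stop the intervention but keep all planned visits. It applies only when treatment is interrupted from six months after the start of DOT.
- Section 6.6 limits the intention-to-treat analysis to those with a minimum of six months on treatment. It separately defines a per-protocol set by 80% of doses.

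At entry, Section 6.3 has no criterion on concomitant drugs. Two of its criteria overlap with the list: "History or treatment for epilepsy" and "Active TB or previous use of INH". Under Section 6.5, medical history comes after the eligibility results: "if eligible, the participant will answer questionnaires containing socioeconomic, medical and criminal history". No rule acts on the answers, and Figure 1 has no row for concomitant medication.

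**The concern.** A drug that might weaken INH is a reason to question exposure. It is not a reason to stop measuring infection. A participant taking one of these drugs can still give blood for IGRA at months 6, 12 and 24. Removing that participant discards an outcome that could have been observed, on an investigator's judgement made after randomisation.

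Two routes lead to the loss, and they differ in what they cost. Use already present at D0 could have been known before randomisation, and withdrawal for it reduces the numbers analysed. Use that starts after D0 could differ by arm. Section 2.5 says of INH that "The most frequent adverse reactions were mild and transient headache, nausea, dizziness", and acetaminophen and aluminum hydroxide are remedies someone with such symptoms might take. If they were taken more often on INH, and those withdrawn differed in infection risk, the comparison of arms would be biased.

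**Working it through.** **Inputs.** Section 6.1.1: 20% latent TB on control and 10% on INH at one year, 5% significance, 90% power, 560 participants, plus 30% = 728. Section 6.1.2: 364 per arm. The frequency of use of the listed drugs is not given, so every withdrawal rate below is an assumption.

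**1. The plan's own figure.** For 20% against 10%, two-sided 5% and 90% power, the pooled normal formula gives 266 per arm (532 in total). With continuity correction it gives 286 per arm (572), which is 12/560 = 2.1% above the stated 560. Then 560 × 1.30 = 728. The point does not depend on this figure; it only sets the scale.

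**2. Who could be affected at baseline.** At an assumed prevalence of 2%, 5% or 10%, 728 × 0.02, 0.05, 0.10 = about 15, 36 or 73 users randomised. Against the 728 − 560 = 168 places added for losses, that is 9%, 22% or 43%. These are upper bounds, because use alone does not meet the Section 6.4 condition.

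**3. Precision.** Power = Φ{(0.10√n − 1.96√(2 × 0.15 × 0.85)) / √(0.20 × 0.80 + 0.10 × 0.90)}. If these withdrawals fall within the planned 30% loss, nothing is added. If they come on top of it:

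| Further withdrawal | n per arm | Power |
|---|---|---|
| 0 | 254 | 88.6% |
| 2 points | 247 | 87.8% |
| 5 points | 236 | 86.3% |
| 10 points | 218 | 83.5% |

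**4. Bias under no true effect.** Let both arms have true risk 0.20, let a fraction w be withdrawn, and let those withdrawn have risk r. The risk observed in those who remain is x = (0.20 − w·r)/(1 − w).

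- Equal withdrawal, w = 5% in both arms: x is the same in each arm, so RR = 1.00 at every r.
- 8% INH, 3% placebo, r = 10%: 0.192/0.92 = 0.2087 and 0.197/0.97 = 0.2031, RR 1.03.
- 8% INH, 3% placebo, r = 40%: 0.168/0.92 = 0.1826 and 0.188/0.97 = 0.1938, RR 0.94.
- 10% INH, 3% placebo, r from 10% to 40%: RR runs from 1.04 to 0.92.

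Bias needs both unequal withdrawal and a different risk in those withdrawn. Its direction depends on whether that risk is above or below average.

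**The case against.** The best defence is that the rule is narrow. It is permissive and requires a dose judged to interfere with INH, so occasional acetaminophen or antacid use does not trigger it. The people judging are blind (Section 6.1.2). Section 6.3 already covers part of the list: the epilepsy criterion can catch valproic acid, carbamazepine and phenytoin taken for epilepsy, and the active-TB criterion can catch rifampicin, cycloserine and ethionamide taken for TB. That is six of twelve entries, at least in part. From month 6 the plan offers continued follow-up. All of this stands, and it limits how many people are affected.

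It does not remove the problem. Blinding limits biased judgement but cannot equalise a trigger that itself differs by arm, and Section 6.1.3 breaks the code for any significant adverse event. Before month 6 there is no stated route to stay.

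Three stronger readings are tempting and not supported:

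- A reader might infer that the missing entry screen makes withdrawal depend on arm. It does not. Baseline use is balanced in expectation by randomisation; only use begun after D0 could differ, and a screen would not prevent that.
- A reader might infer a bias favouring INH, for example by giving 5% of the INH arm, all withdrawn, a 20% risk: (0.10 − 0.05 × 0.20)/0.95 = 0.0947, RR 0.474 instead of 0.50. Withdrawing 5% of placebo at 20% risk as well leaves placebo at 20% and the RR at 0.474. The shift comes from the assumed risk in those withdrawn, not from unequal withdrawal, and the documents do not support that risk.
- A reader might take Section 2.5 as evidence of more remedy use on INH. It calls the symptoms mild and transient, gives comparative rates only for hepatitis, and describes a different regimen from this trial's.

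Nor is it a flaw that the rule applies to placebo participants, since a blinded rule has to apply to both arms.

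**Conclusion.** The point holds in a limited form. The documents allow a randomised participant to lose the primary outcome because of concomitant-drug use at a dose judged to interfere with INH, although nothing about that use stops the outcome being measured. The six-month condition in Section 6.6 completes the loss: anyone withdrawn before then leaves the main analysis.

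The likely effect is modest. Precision falls by about 2 points of power for 5 further points of withdrawal (88.6% to 86.3%). Under no true effect and 8% against 3% withdrawn, the RR lies between about 0.94 and 1.03. These figures rest on assumed rates of use and assumed risks in those withdrawn. The actual size and direction are unknown. The change is worth making because the loss is avoidable at little cost.

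**What to change.** - In Section 6.4, remove concomitant-drug use as a reason to leave the trial. Record the drug and the date, and leave decisions about study drug with clinicians as now.
- Keep these participants in every scheduled IGRA and sputum visit, whenever the use occurs.
- In Section 6.6, analyse them in their randomised arm without the six-month treatment condition. Without this change, anyone whose study drug stops early would still drop out of the main analysis. Use the drug record only to define the per-protocol set.
- Reconcile Sections 6.3 and 6.4 on concomitant drugs, and ask about current medicines before randomisation. Whether any drug should bar entry is the sponsor's clinical decision.

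**Cost.** One screening question, a data field and wording edits; the required sample size does not change. Some participants with a listed drug stay in the main analysis, which may slightly dilute the effect. As an illustration, if INH did nothing in 5% of its arm and the planned 10% held in the rest, the INH risk would be 0.95 × 0.10 + 0.05 × 0.20 = 0.105, and the RR 0.525 instead of 0.50.

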#### 6.1.1 Sample and population of the study

This research will be carried out at one prison unit, located in the city of Dourados, in the state of Mato Grosso do Sul. Currently, this prison unit has approximately 2,300 inmates, with a mean age of  $31.5 \pm 9.4$  years; an average of  $9.7 (\pm 4.2)$  individuals per cell, who remain in a closed regimen, about  $20.8 (\pm 24.1)$  months. The TB indicators show a tuberculin test seroconversion rate of 26% (23-26) and incidence, 2.45 / 100,000(28).

The sample was calculated for a significance level of 5%, detection power of 90%, considering a percentage of occurrence of latent TB of 20% in the control group after one year of follow-up and 10% in the experimental group. For these parameters, 560 individuals will be needed for the study, however, 30% will be added for possible losses, ending the sample in 728 participants. Memory calculation available at <https://www.sealedenvelope.com/power/binary-superiority/>.

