Clínical evaluation	X	X	X	X	X	X	X	X
Adverses events evaluation			X	X	X	X	X	X

DOT = Directly Observed Treatment, mo = months, d = days

Figura 1 - Schedule, second quarters, of research activities. The parentheses indicate that the procedures are optional.

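### IGRA and sputum are optional at the early exclusion visit, so infections acquired since the last scheduled test go unmeasured in participants who leave

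*Combined protocol and SAP*

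**What the plan says.** Section 6.4 calls for a visit at withdrawal with clinical and adverse-event evaluation, but on samples it says "blood and / or sputum collection should be performed according to the clinical judgment". Figure 1 matches. In the early exclusion column the two evaluations carry a plain X, while IGRA and sputum carry (X); the caption explains: "The parentheses indicate that the procedures are optional". No section makes the exit IGRA mandatory or gives criteria for ordering it.

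Section 5.1 measures the primary outcome by IGRA, and section 5.2 measures active TB by sputum culture. After enrolment, IGRA is scheduled only at months 6, 12 and 24 (section 6.5). Section 6.6 counts a latent-TB seroconversion only in month 12 or 24, and limits the analysis it calls intention-to-treat to people with at least 6 months of treatment.

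Transfer and early release are listed withdrawal reasons in section 6.4. Section 6.1.1 describes the prison as holding on average 9.7 "individuals per cell, who remain in a closed regimen, about" 20.8 (± 24.1) months. For sample size, the same section assumes "latent TB of 20% in the control group after one year of follow-up and 10% in the experimental group", states that "560 individuals will be needed for the study", and adds that "30% will be added for possible losses".

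**The concern.** Section 2.1 describes latent infection as clinically silent. A clinician examining a leaver therefore has no sign by which to pick out someone who has converted. Leaving the test to clinical judgment means either that the primary measurement is not taken, or that it is taken for reasons unrelated to infection.

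Someone with a negative month-6 IGRA who leaves at month 11 contributes nothing about the last five months. Someone who leaves at month 5 contributes no post-baseline IGRA at all. The notification system in section 6.5 is used to identify active TB, so it does not recover latent infections. Once the participant has gone, no choice of analysis can restore the result. What is at stake is primary-outcome events in a trial that plans for substantial loss.

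**Working it through.** **Inputs from the protocol.** Conversion 20% (control) and 10% (isoniazid) at one year, 5% significance, 90% power, 560 evaluable plus 30% = 728 (section 6.1.1); 364 per arm (section 6.1.2); IGRA at months 6 and 12 (section 6.5).

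**The plan's sample size.** Taking the test as two-sided (the plan does not say), the pooled formula per arm is [1.96·√(2·0.15·0.85) + 1.2816·√(0.16 + 0.09)]² / 0.10² = 266. With the continuity correction it is 286, or 572 in total, which is within about 2% of the stated 560. Then 560 × 1.3 = 728. The allowance is 728 − 560 = 168 people, or 168/728 = 23.1% of those randomised.

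**Infections missed since the last scheduled IGRA.** Assumptions: exit times are exponential with monthly rate λ; infection has a constant monthly hazard μ = −ln(1 − risk)/12, that is 0.01860 for control and 0.00878 for isoniazid; month-6 positives count as observed.

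The chance of being infected and then leaving within one 6-month interval is

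s = (1 − e^(−6λ)) − [λ/(λ+μ)]·(1 − e^(−6(λ+μ))).

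Missed before month 6: 364·s. Missed between months 6 and 12: 364·e^(−6(λ+μ))·s.

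Worked case, control arm at the plan's own allowance: λ = −ln(560/728)/12 = 0.02186. So s = 0.12294 − 0.5404 × 0.21554 = 0.00647. Missed before month 6: 364 × 0.00647 = 2.35. Missed later: 2.35 × 0.784 = 1.85. Total 4.2.

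The other two rows read the stay in section 6.1.1 as a mean remaining stay of 20.8 months, or as a residual mean of (24.1² + 20.8²)/(2 × 20.8) = 24.4 months, with ± 24.1 taken as a standard deviation.

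| Exit assumption | Leave before month 12 | Missed, placebo / INH | Of these, before month 6 | Months 6–12 | Observed, placebo / INH |
|---|---|---|---|---|---|
| 168 losses | 23% (168) | 4.2 / 2.1 | 2.4 / 1.1 | 1.9 / 0.9 | 60 / 30 |
| Mean 24.4 months | 39% (283) | 7.0 / 3.4 | 4.1 / 2.0 | 2.9 / 1.5 | 51 / 25 |
| Mean 20.8 months | 44% (319) | 7.8 / 3.8 | 4.7 / 2.3 | 3.1 / 1.6 | 48 / 24 |

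The missed conversions are about 7%, 14% and 16% of those observed. Between 55% and 60% of them are in people who leave before month 6.

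**A second exit model.** Let 30% (109 per arm) leave uniformly over 12 months, with the linear risk that section 6.7 assumes. The mean gap since the last IGRA is 3 months. Missed: 109.2 × 0.20 × 3/12 = 5.5 control and 109.2 × 0.10 × 3/12 = 2.7 isoniazid. The size does not hinge on the exponential form.

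**Effect on the comparison.** This uses the second model, all 364 per arm as denominator, untested leavers counted as uninfected and exit positives counted. Detected infections per arm are 254.8·r + 109.2·(0.25·r + q·0.25·r), where r is the yearly risk and q the share tested at exit.

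| Exit testing, INH / control | Detected, INH / control | RR | Power |
|---|---|---|---|
| 0% / 0% | 28.2 / 56.4 | 0.50 | 0.905 |
| 100% / 100% | 30.9 / 61.9 | 0.50 | 0.932 |
| 80% / 20% | 30.4 / 57.5 | 0.53 | 0.87 |
| 20% / 80% | 28.8 / 60.8 | 0.47 | 0.95 |
| 100% / 0% | 30.9 / 56.4 | 0.55 | 0.83 |
| 0% / 100% | 28.2 / 61.9 | 0.46 | 0.97 |

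Equal under-testing costs events and leaves the RR at 0.50. Only testing that differs by arm moves it.

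**The case against.** Several points on the other side stand.

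- A reader might infer that selective exit tests distort the incidence or the RR. The documents do not support that as a general claim. Under section 6.6 an exit IGRA outside month 12 or 24 is not an endpoint, whether positive or negative. Even if it were counted, bias in the RR needs testing that differs by arm, and section 6.1.2 blinds everyone but the pharmacist. A narrower route remains: tests prompted by adverse events could be more frequent on isoniazid, and section 6.1.3 breaks the blind for significant events.
- A reader might infer that transfer and release are the main route of loss. The documents give no breakdown of losses. Section 6.1.1 does not say whether 20.8 months is completed stay, time served so far or expected stay.
- Under the analysis set as written, a mandatory exit test could add only the conversions in leavers after month 6: about 2–3 placebo and 1–2 isoniazid. The seroconversion rule would still have to change before even these counted.
- A reader might expect exit tests after month 12 to supply much of the evidence on residual protection (section 4.2). A test soon after month 12 says little about protection up to a year after treatment.
- The sputum gap is partly covered by the notification system, and none of the figures here quantify it.
- Some leavers will be absent or will refuse. Section 6.4 also lets those whose treatment stops from month 6 onward leave without further collections.

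These points reduce the size of the concern but do not remove it: the visit exists, lists both tests, and leaves them to a judgment that cannot detect the outcome.

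**Conclusion.** The point holds as a loss of information. The protocol text and Figure 1 agree that the exit IGRA and sputum are optional, and nothing elsewhere cures it. At the plan's own 168 losses, about 4 placebo and 2 isoniazid conversions go unmeasured; if 39–44% leave before month 12, it is 7–8 and 3–4. The uniform-exit illustration, with all randomised participants analysed, puts the power at stake at under three percentage points.

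These figures rest on assumed exit times, on the plan's 20% and 10% risks, and on every leaver being available for testing, so they are upper limits on what an exit test could recover within each scenario. Making the test mandatory without amending section 6.6 would add no event to the primary analysis. Weight: minor to moderate, worth doing because it is cheap and the data cannot be recovered later.

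**What to change.** 1. **Figure 1 and section 6.4.** Change (X) to X for IGRA and sputum at the early exclusion visit for every participant who has started DOT, is present and consents. Exempt anyone with an IGRA in the previous 30 days. In section 6.4, remove the reliance on clinical judgment for these two tests, and keep the participant's right to leave without additional collections.

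2. **Section 6.6.** Extend the seroconversion definition beyond months 12 and 24. A positive exit IGRA counts as a conversion at its date, and a negative one extends person-time to that date. Include these results for all randomised participants, not only those with at least 6 months of treatment.

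Cost: an amendment to the schedule, section 6.4 and section 6.6, and at most one IGRA and one culture per leaver at a visit that already lists both. Unannounced releases, refusals, and indeterminate or contaminated samples that cannot be repeated will remain missing; report their number by arm.
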